# Protocol

### 1. Background

Metabolic dysfunction-associated steatotic liver disease (MASLD) often coexists with type 2 diabetes (T2DM) because of their common risk factors. With the global epidemic trend of obesity and T2DM, MASLD has become an important cause of chronic liver disease in developed countries and rich areas in China. At present, the prevalence of MASLD in Chinese adults is 6-27%. Compared with non-MASLD patients, the relative risk of type 2 diabetes in patients with MASLD is 1.86. For patients with elevated blood glucose, the strategy of reducing liver fat content could also alleviate insulin resistance, contribute to better glucose control, and delay the occurrence of diabetes complications. Due to the unclear pathogenesis, there is a lack of effective medication for MASLD. Lifestyle intervention is still the main treatment. Weight loss of 7-10% can effectively reduce liver steatosis and inflammation.

Calorie restriction (CR) is an effective method to reduce weight and severity of obesity related diseases, but traditionally it requires constant effort to cut down calorie intake every day (continuous calorie restriction, CCR) and may lead to potential adverse effects on the body. Intermittent calorie restriction (ICR) refers to maintaining no or very-low calorie intake periodically, which means alternating normal diet and fasting for a certain period to prevent and treat various diseases. The most common ICR schemes include time restrict fasting (TRF) or time restrict eating (TRE), alternate day fasting (ADF) and fasting for two days per week (5:2 diet). ICR can effectively reduce weight, lower blood pressure, improve lipid profile and reduce oxidative stress. It also facilitates glucose control by increasing insulin sensitivity and improving  $\beta$  Cell function. Recent studies have proved the effectiveness of TRE and ADF on reducing weight and improving cardiometabolic risk factors. However, effect of ICR, especially 5:2 diet, on MASLD patients has been rarely studied. A few studies have found ICR could reduce liver enzymes in MASLD patients, but they were less accurate because fat content of the whole liver, as well as of different liver segments were not quantitatively evaluated before and after treatment. More importantly, no study directly compared the therapeutic effect of ICR and CCR on MASLD currently.

2. Aim of the study

In the present study, we carried out a randomized, controlled, open-label clinical trial to investigate the efficacy and safety of ICR in MASLD patients with abnormal glucose metabolism. For ICR group, we adopt the 5:2 scheme which was related to stronger patient compliance. The control group received traditional CCR. Two groups were instructed to keep overall calorie restriction to similar degree during 12 weeks of treatment. The changes of LFC of the whole liver, as well as of different liver segments measured by MRI-Proton Density Fat Fraction (MRI-PDFF) were compared between two groups. We hypothesize that ICR will be more effective than CCR in reducing LFC and other metabolic risk factors.

- 3. Research design
- 3.1 Overall design

This 12-week, open-label, randomized, controlled, parallel-group trial was conducted at Zhongshan Hospital Fudan University between July 2020 and July 2021 (ClinicalTrials.gov, NCT04283942). The trial was initiated by the researcher, performed in accordance with the ethical principles of the Declaration of Helsinki and approved by the Ethics Committee of Zhongshan Hospital Fudan University (approval number: B2019-256). A total of 60 patients were enrolled in the trial, and written informed consent was obtained from all patients. 3.2 Randomization and masking

The simple randomization method was used to ensure similar baseline characteristics between two groups. The randomization scheme will be provided by the Statistics Department of School of Public Health of Fudan University (generated by SAS software), and randomization will be completed by staff unrelated to this trial. According to the randomization scheme, a random envelope marked with the treatment number will be made and assigned for each subject according to the order of enrollment. The treatment will be carried out according to the arrangement of corresponding scheme.

- 4. Study participants
- 4.1 Inclusion Criteria
- Age 18-70
- Diagnosed as fatty liver by ultrasound or magnetic resonance imaging
- BMI ≥ 24 kg/m^2
- Abnormal glucose metabolism: (meeting at least one):
  - Impaired glucose regulation: fasting blood glucose ≥ 100 mg/dL, postprandial blood glucose ≥ 140 mg/dL or HbA1c ≥ 5.7%
  - 2) Diabetes mellitus: diabetic symptoms + plasma glucose concentration ≥ 200 mg/dL at any time or fasting plasma glucose concentration ≥ 100 mg/dL or OGTT 2 h plasma glucose concentration ≥ 200 mg/dL

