5.1 Dietetic intervention

- ICR group: Participants in ICR group were instructed to ensure 2 successive days of fasting-mimicking and 5 days of recovery per week. On fasting-mimicking days, the participants were instructed to consume approximately 500 kcal/day and they were provided with plant-based meal replacement (ZhenBaiNian nutrition bar, Beijing Winlife Research Institute of Nutrition, Health, Food Science, and Technology, China) to improve adherence and ensured adequate intake of micronutrients. In the rest 5 days of recovery per week, participants were allowed to consume their usual diet. Main ingredients of this meal replacement are as follows:
  - Main ingredients: isomaltooligosaccharide solution, high-protein and high-fiber crispy grain (soy protein isolate, rice, polydextrose, calcium carbonate), Chia seed, resistant dextrin, coconut potato, salty vegetable grain, etc.

Table 1. Information of nutrition bar used in this trial			
	Per 100g	%NRV	

energy	355.4 kcal	18%
protein	15.4 g	26%
Fat	12.4 g	21%
Trans fats (acids)	0 g	
Polyunsaturated fatty acids	3.6 g	
carbohydrate	34.0 g	11%
dietary fiber	23.5 g	94%
sodium	261 mg	13%
vitamin A	565 µg	71%
vitamin D	2.5 µg	50%
vitamin E	8.05 mg	58%
Vitamin B1	1.30 mg	93%
Vitamin B2	1.30 mg	93%
Vitamin B6	1.30 mg	93%
Vitamin B12	0.80 µg	33%
vitamin C	67.7 mg	68%
nicotinic acid	13.50 mg	96%
folic acid	328 µg	82%
Pantothenic acid	3.17 mg	63%
Biotin	3.8 µg	13%
phosphorus	257 mg	37%
potassium	318 mg	16%
magnesium	72 mg	24%
calcium	433 mg	54%
iron	6.7 mg	45%
zinc	5.25 mg	35%
selenium	10.0 µg	20%
copper	0.44 mg	29%
fluorine	0.06 mg	6%
manganese	1.00 mg	33%
ω~ 6 Linoleic acid	1.6 g	
ω~ three α- linolenic acid	2.0 g	

Manufacturer: Beijing Wanlaikang Nutrition and Health Food Science and Technology Research Institute Co., Ltd

Product standard No.: Q/CPKWC 0085

> Food production license No.: SC10611141312769

 CCR group: Participants in CCR group were instructed to consume the prescribed calories (25 kcal / kg × [height (cm) – 100] kg) every day by eating conventional food without time restriction.

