Both groups received dietary counseling from experienced nutritionists during the trial. Kitchen scales were distributed to participants, and they were encouraged to weigh food to ensure accurate reporting of their caloric intake. During the trial, all the participants were required to write daily dietary log. Using each log, nutritionists assessed their calorie intake each day based on the nutrient content shown on the Chinese Food Composition Table.Participants received face-to-face instruction or app messages every week to assess their adherence to the prescribed diet.

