6.3 Other pre-specified outcomes

- Change of fat mass and lean mass measured by a bioimpedance analyzer
- Change of abdominal adiposity measured by MRI: visceral adipose tissue and subcutaneous adipose tissue
- Change of liver stiffness measured by liver transient elastography
- Change of insulin sensitivity: fasting insulin and HOMA-IR (fasting glucose in mmol/L x fasting insulin in  $\mu$ U/mL)/22.5)
- 7. Follow-up visits
- (1) Screening visit (V0): The purpose of this visit is to confirm subjects' eligibility and interest in the proposed study, and obtain informed consent, relevant medical history (including diabetes, fatty liver, alcohol drinking history, hepatitis history, drug use, etc.), physical measurements (weight, height, waist circumference and blood pressure), and laboratory measurements (OGTT, HbA1c, liver and renal functions, electrolytes, hepatitis markers, etc). H-Proton Magnetic Resonance Spectroscopy (H-MRS), MRI-Proton Density Fat Fraction (MRI-PDFF) and liver transient elastography were applied to evaluate the fatty liver. Body composition analysis and other examinations were performed. Relevant laboratory and imaging examination results within 2 weeks before screening can be approved.
- (2) Baseline visit (V1): The baseline follow-up was scheduled within 2 weeks after the screening period. Physical examination was conducted. Subjects will be required to record their diet and steps for 3 days before day 0 and the average of calorie consumption and steps will be used as baseline reference. Randomization will be conducted.
- (3) Follow up and termination visits (V2 V9): At each visit, diet and step records will be collected. At week 2, 4, 8 12, physical measurements, fasting glucose and adverse events will be recorded. Nutritionists will provide dietary advice and help subjects to keep calorie

restriction and a balance of nutrients. On this basis, liver and renal functions, electrolytes, fasting blood glucose and lipids profiles will be measured at week 4. At week 12 (termination visit), OGTT, H-MRS, MRI-PDFF, liver transient elastography and body composition analysis will be added. At week 1, 3, 6, 10, only telephone follow-up will be conducted.

(4) Post-intervention visit (V10): At 4 weeks after the intervention (week 16), body weight will be investigated by telephone.

	Screening	Baseline								Termin ation	Post- interve ntion
Visit	V0	V1	V2	V3	V4	V5	V6	V7	V8	V9	V10

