#### 11. Statistics

#### 11.1 Statistical power and sample size

A 12-week ICR has been reported to result in approximately 7% weight loss in overweight and obese participants, while the CCR group caused 30% less weight loss than the ICR group. According to previous studies, a 7% weight loss was approximately accompanied with a 19.3% reduction in LFC. Thus, a priori power calculation assumed 19.3% and 13.5% reduction in LFC in the ICR and CCR groups, respectively. Assuming an anticipated dropout rate of 15%, we estimated that an enrollment target of 60 participants (30 per group) would provide the trial with 80% statistical power to detect a significant difference of  $5.8\pm8\%$  in absolute LFC change between ICR and CCR group at a significance level of 0.05 using a two-tailed test.

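### Does the stated aim of similar calorie restriction need correcting because the two diets are prescribed by different rules?

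*Combined protocol and SAP*

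**What the plan says.** Section 2 (Aim of the study) states: "Two groups were instructed to keep overall calorie restriction to similar degree during 12 weeks of treatment". Section 5.1 gives the two prescriptions.

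- **ICR:** about 500 kcal/day on two successive days each week. For the other days, "In the rest 5 days of recovery per week, participants were allowed to consume their usual diet".
- **CCR:** "Participants in CCR group were instructed to consume the prescribed calories", set at 25 kcal/kg times (height in cm minus 100) kg, every day.

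Section 5.1 also describes monitoring common to both arms: counselling by nutritionists, kitchen scales, and a daily log from which "nutritionists assessed their calorie intake each day". Participants are contacted weekly "to assess their adherence to the prescribed diet". Section 7 adds a 3-day record before day 0, of which "the average of calorie consumption and steps will be used as baseline reference", and says of the follow-up visits: "Nutritionists will provide dietary advice and help subjects to keep calorie" restriction. Section 8 repeats the baseline and daily recording for both groups.

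Calorie intake is not listed among the outcomes in sections 6.1 to 6.3. Section 11.2 does not name it either, but it applies a generalized linear model, adjusted for age, sex and baseline, to between-group differences in change for continuous variables generally.

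**The concern.** The ICR deficit depends on what a person usually eats, and the CCR target depends only on how tall that person is. Neither rule is calibrated to the other or to the 3-day baseline record, and similar degree is given no number or tolerance. On its face, section 2 claims something that section 5.1 does not secure.

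What would be at stake is interpretation. Section 11.1 builds the planned effect on a report that "the CCR group caused 30% less weight loss than the ICR group". If the ICR prescription happened to impose a larger deficit, a difference in liver fat could reflect how much was cut and not the 5:2 pattern. A reader told that restriction was similar, and shown no intake by arm, would credit the pattern.

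**Working it through.** The documents state no figure for the degree of restriction in either arm, so there is none to reproduce. The related planning figure does reproduce: 19.3% × 0.7 = 13.5%, and 19.3 − 13.5 = 5.8 (section 11.1).

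**Inputs from section 5.1.** ICR: 500 kcal on 2 days and usual intake U on 5 days. CCR: C = 25 × (height − 100) kcal/day, which is 1,500, 1,625 and 1,750 at 160, 165 and 170 cm.

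**Assumed inputs, not in the documents.** Mean height 160 to 170 cm; mean U 1,800 to 2,500 kcal/day.

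**Step 1: weekly prescribed deficit.** ICR = 2(U − 500). CCR = 7(U − C). Setting them equal gives 5U = 7C − 1,000, so U = 1.4C − 200. Break-even U is 1,900, 2,075 and 2,250 kcal/day at the three heights, all inside the assumed range.

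**Step 2: prescribed cut as a percentage of U.** ICR = (2/7)(1 − 500/U). CCR = 1 − C/U.

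| U (kcal/day) | ICR | CCR, 160 cm | CCR, 165 cm | CCR, 170 cm |
|---|---|---|---|---|
| 1,800 | 20.6% | 16.7% | 9.7% | 2.8% |
| 2,000 | 21.4% | 25.0% | 18.8% | 12.5% |
| 2,200 | 22.1% | 31.8% | 26.1% | 20.5% |
| 2,500 | 22.9% | 40.0% | 35.0% | 30.0% |

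ICR is nearly constant. CCR lies on either side of it.

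**Step 3: which direction.** Break-even U is linear in height and averages (1,900 + 2,250)/2 = 2,075 over 160 to 170 cm. The share of the assumed rectangle in which CCR restricts more is (2,500 − 2,075)/(2,500 − 1,800) = 425/700, about 61%. This is an area, not a probability, but it shows that the prescriptions do not systematically favour ICR.

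**Step 4: link to the 30% figure.** Suppose weight loss is proportional to deficit (a further assumption).

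- A CCR deficit equal to 70% of the ICR deficit needs 7(U − C) = 1.4(U − 500), so U = 1.25C − 125. That is 1,906 kcal/day at 165 cm and 2,063 at 170 cm, with gaps of 121 and 134 kcal/day. At 160 cm it would need U = 1,750, outside the assumed range; at U = 1,800 the ratio is 300/371 = 81%.
- The mirror case, a CCR deficit equal to 130% of the ICR deficit, needs U = (7C − 1,300)/4.4 = 2,091, 2,290 and 2,489. It is reached at all three heights.

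**Step 5: what an intake table could show.** With an assumed between-person SD of 300 to 500 kcal/day, the 95% half-width for an arm difference, t × SD × √(2/n), is 155 to 258 kcal/day at 30 per arm. After 15% dropout (25.5 per arm) it is 169 to 281. Both ranges are wider than the 121 to 134 kcal/day gap in Step 4.

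**The case for a change.** The strongest case for a change is that the hypothesis is ICR superiority, that the effect size is borrowed from a difference in weight loss, and that the only numeric instructions do not produce equal restriction by construction. Weekly review checks adherence to each arm's own prescription, so counselling need not pull the arms together. The logs are already scored, so a by-arm summary would cost little.

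Part of this stands. The prescriptions do not guarantee similarity, no common target is written, and intake is not named in sections 6.1 to 6.3 or 11.2. A report that attributed a liver-fat difference to the 5:2 pattern at equal calories, without showing intake, would go beyond the evidence.

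The rest does not carry. Different formulas can give similar averages, and the documents do not show that they failed to. The imbalance could as easily work against ICR as for it. The sentence in section 2 describes an instruction to participants; no hypothesis test, primary outcome or model term depends on it. The general model sentence in section 11.2 can already take change in intake. A table of self-reported intake would also be too imprecise, and too exposed to selective logging, to settle whether restriction was similar.

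**Conclusion.** No change to the plan is called for. The documents leave similar restriction unsecured but not contradicted. Break-even falls inside a plausible range of usual intake, and the prescribed cuts may agree or differ either way: at 170 cm, 21.4% (ICR) against 12.5% (CCR) at 2,000 kcal/day, equal at 2,250, and 22.9% against 30.0% at 2,500. These figures rest on assumed height and usual intake. The tie to the 30% weight-loss ratio also assumes weight loss proportional to deficit, and it holds in the ICR-favouring direction at only two of the three heights.

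The randomised comparison of the two regimens is valid whatever the achieved intakes were. What remains is missing detail that a competent analyst fills: describe intake by arm from logs already scored, with the number of logged days and, for ICR, of fasting days. That summary should be read as description, not as a covariate or as proof of similarity. Section 3.1 describes the trial as already conducted, so a commitment added after the data were seen would be post hoc in any case. No view is taken here on either diet rule.

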4.3 Termination criteria

- Request to withdraw informed consents
- Pregnancy
- Systolic blood pressure ≥ 180 mmHg and diastolic blood pressure ≥ 110 mmHg
- Liver enzymes (ALT or AST) increase to ≥ 6 times of the upper normal limit and last for 4 weeks
- Fasting blood glucose increases to > 200 mg/dL and lasts for 4 weeks
- Serum creatinine increases to ≥ 1.5 mg/dL
- During the treatment, drugs which may affect liver fat content are added or adjusted for dosage: such as hypoglycemic drugs, lipid-lowering drugs and liver protecting drugs
- 5. Intervention

After a 2-week screening phase, a total of 60 eligible patients will be randomized 1:1 into ICR and CCR group.

Figure 1. Study design

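### Does simple randomisation of 60 patients leave the trial without the balance and the 30 per group that it plans for?

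*Combined protocol and SAP*

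**What the plan says.** Section 3.2 gives the method and its purpose in one sentence: "The simple randomization method was used to ensure similar baseline characteristics between two groups". On how the list was made it says "The randomization scheme will be provided by the Statistics Department of School of Public Health of Fudan University (generated by SAS software"), and on its use, "a random envelope marked with the treatment number will be made and assigned for each subject according to the order of enrollment". It mentions no blocks, strata or minimisation factors. It also does not say whether the list was a series of independent draws or one random permutation with fixed totals.

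Section 5 says that "a total of 60 eligible patients will be randomized 1:1 into ICR and CCR group". Section 11.1 says that "an enrollment target of 60 participants (30 per group) would provide the trial with 80% statistical power" for a difference of 5.8 with SD 8, two-sided at 0.05.

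Section 11.2 compares the groups on change with generalized linear models adjusted for age, sex and baseline measures. Section 7 places MRI-PDFF at screening (V0) and randomisation at the baseline visit (V1), so liver fat content (LFC) is known before allocation. Section 3.1 describes the trial in the past tense, as run from July 2020 to July 2021 with 60 patients enrolled.

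**The concern.** Simple randomisation in the textbook sense allocates each patient independently. It balances baseline characteristics only in expectation and fixes neither arm size. With 60 patients, chance departures are common, so the verb in Section 3.2 and the group size in Section 11.1 both seem to promise something that the method cannot guarantee.

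Two consequences would matter if they were large. Unequal arms lose precision. An imbalance in a prognostic factor makes a small open-label trial harder to read, and the model adjusts for only a short list of covariates. Glycaemic category (impaired regulation or diabetes, both eligible under Section 4.1), baseline calorie intake and step count are neither stratified nor named in the model. Since LFC is available before allocation, permuted blocks stratified by screening MRI-PDFF look like an inexpensive improvement that was missed.

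**Working it through.** **Inputs.** N = 60 and 1:1 (Section 5); 30 per group, difference 5.8, SD 8, two-sided alpha 0.05, 15% dropout (Section 11.1); adjustment for age, sex and baseline measures (Section 11.2).

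**1. The plan's own figure.** At 30 per arm with everyone analysed, SE = 8 × √(1/30 + 1/30) = 2.066. The standardised effect is 5.8 / 2.066 = 2.808, and power = Φ(2.808 − 1.960) = 80.2%. The stated 80% is therefore reproduced only when all 60 contribute. With 15% dropout (25.5 per arm) the same formula gives 73.5%. That shortfall concerns dropout. It exists at 30:30 and does not come from the randomisation method.

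**2. Arm sizes under independent tosses.** With X ~ Binomial(60, 0.5):

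| Split | Probability |
|---|---|
| exactly 30:30 | 10.3% |
| 25:35 or worse | 24.5% |
| 22:38 or worse | 5.2% |

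**3. What unequal arms cost.** Power = Φ(5.8 / [8√(1/a + 1/(60 − a))] − 1.960), all 60 analysed:

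| Split | SE | Power |
|---|---|---|
| 30:30 | 2.066 | 80.2% |
| 25:35 | 2.095 | 79.1% |
| 22:38 | 2.143 | 77.2% |

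Averaged over the binomial distribution of splits, power is 79.5%, a loss of 80.2 − 79.5 = 0.7 points. With 15% dropout the comparison is 73.5% against 72.8%, again 0.7 points.

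**4. Chance imbalance in one continuous factor.** At 30:30 the standardised difference has SD √(2/30) = 0.258. So P(|difference| ≥ 0.3 SD) = 2[1 − Φ(0.3/0.258)] = 24.5%, and for 0.5 SD it is 5.3%. Averaged over independent-toss splits the figures are 24.9% and 5.5%. Forcing equal arms alone therefore does almost nothing for covariate balance.

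**5. What stratified blocks would add.** This was simulated with 60 patients and 20,000 runs per method. The documents give no baseline distribution, so the covariates are assumed normal, the LFC cut is at the median, and blocks are of 4 or 6.

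| P(imbalance of 0.3 SD or more) | Simple | Stratified blocks |
|---|---|---|
| baseline LFC | 25% | 6% |
| a factor unrelated to LFC | 25.0% | 24.0% |

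The gain falls almost wholly on LFC, whose baseline value is already in the model. Once it is adjusted for, the SE of the treatment effect is 1.8% above the ideal under simple randomisation and 0.4% above it under stratified blocks, a gain of about 1.4%. This figure includes the effect of unequal arms. Carried into the power formula at 60 analysed, 2.808/1.018 = 2.758 gives 78.8% and 2.808/1.004 = 2.797 gives 79.9%. The whole redesign is thus worth about 1.1 points of power.

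**The case for a change.** The best case for acting is that the sentence in Section 3.2 is untrue as written. The trial has little slack (73.5% power after the stated dropout), and stratified blocks of random size cost almost nothing when a list is generated. They would cut the chance of a 0.3 SD imbalance in baseline LFC from about 25% to 6%. A reader also cannot tell how the sequence was produced, and several plausible prognostic factors lie outside the model.

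Part of this stands. The verb claims more than simple randomisation delivers, and the algorithm is not described.

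The rest does not carry a change:

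- The LFC benefit lies in a variable that the primary comparison already adjusts for, so what is left is the 1.4% in SE.
- The factors outside the model are the ones that the proposed stratification does not help, unless they track LFC closely.
- Chance imbalance under a valid random allocation biases neither the estimate nor the P value.
- The statement that the method cannot give 30 per group goes too far. Section 11.1 calls that number an enrolment target, and a list made in SAS by a statistics department may have been a permutation with exactly 30 of each. The text leaves this open.
- Restriction has a price. Independent draws are the least predictable scheme, which is worth something where staff see each allocation at one site and envelopes are used in order of enrolment. Random block sizes reduce that cost but do not remove it.

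**Conclusion.** The concern does not call for a change. The literal criticism of the word in Section 3.2 is right: balance holds in expectation, and 30 per group is likely only approximately if the list was made by independent draws. But the choice is a fair trade-off with almost no gain on the other side. Equal arms are worth about 0.7 points of power on average and 3.0 points at 22:38 (80.2 − 77.2), a split that is reached or exceeded in 5.2% of lists. Stratified blocks as a whole would lower the adjusted SE by about 1.4%. There is no bias to correct. Because Section 3.1 reports enrolment as complete, the allocation could not be redone anyway.

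The missing detail about the list is a reporting gap, and the analysis in Section 11.2 runs in the same way whichever algorithm was used. The sizes rest on the Section 11.1 inputs (5.8, SD 8) and on independent tosses as the least favourable reading of the list. The SE figure also assumes normal covariates and a median cut. If the list was a fixed 30/30 permutation, the arm-size part of the concern disappears entirely. The loss of power from dropout is a separate matter and adds no weight here.

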# 5.2 Physical activity

During the trial, all participants were required to maintain their exercise routines and record their daily steps using a unified pedometer (Redmi Smart Band, Xiaomi Corporation, China). The use of drugs affecting blood glucose and fatty liver were avoided.

- 6. Study outcomes
- 6.1 Primary outcome
- Change in liver fat content from baseline to 12 months

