Physical measurements: At the clinic visit, trained staff will take measurements of body weight, height, waist circumference, blood pressure according to standard procedures. Subjects should avoid wearing shoes and heavy clothes when measuring body weight. Mid-way between the lower border of rib margin and the upper border of iliac crest will be measured as waist circumference. The blood pressure will be measured after resting for 5 minutes in a sitting position and alcohol, cigarettes, coffee/tea and physical exercise will be avoided within 30 minutes before the measurement. Automatic sphygmomanometer will be applied for standardized detection.

Laboratory measurements: Blood samples will be drawn 10 hours after fasting and be used to measure blood glucose, HbA1c, liver enzymes, serum creatinine, urine acid and lipids.. High performance liquid chromatography (HPLC) method will be used for measuring HbA1c. Total cholesterol, high-density lipoprotein cholesterol, triglycerides, free fatty acids, electrolytes, liver enzymes, serum creatinine and urine acid will be measured by a model 7600 automated bioanalyzer (Hitachi, Tokyo, Japan). Low-density lipoprotein cholesterol will be calculated by the Friedewald equation. The FBG and 2-hour postprandial blood glucose in oral glucose tolerance test will be tested following a standard 75g oral glucose tolerance test and measured using the glucose oxidase method. An electrochemiluminescence immunoassay will be used to measure the fasting and 2-hour postprandial insulin. All parameters are tested in the clinical biochemical laboratory of Zhongshan Hospital affiliated to Fudan University. The clinical testing laboratory will adopt the standardized process and obtain the corresponding certification qualification.

H-MRS: Whole liver fat content by H-MRS was performed with a 1.5T MRI Scanner (Siemens Healthineers, Germany). Firstly, T1-weighted sagittal, coronal, and axial images were acquired for the localization of the spectroscopy acquisition voxel. A single 2×2×2 cm voxel was placed within the right lobe avoiding major vascular structures and subcutaneous fat tissue. The proton spectrum was acquired after shimming over the volume of interest by means of a point-resolved spectroscopy sequence with the following parameters: repetition time = 1500 ms and echo time = 135 ms. Signal intensities of the water peak at 4.8 ppm (Sw) and the fat

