Transient elastography: The controlled attenuation parameter (CAP) in dB/m and Liver stiffness measurement (LSM) in kPa will be measured using FibroScan (FibroScan 502 Touch, Echosens, France). All subjects will be detected when holding breath in supine position by using the M probe. Each subject collected at least 10 valid measurements. Only when the proportion of effective measurement times to the total measurement times is  $\geq$  60%, the interquartile range (IQR) of repeatedly collected CAP value is  $\leq$  40 dB / m, and the IQR of repeatedly collected LSM value is  $\leq$  30%, can the result be considered reliable. The median value will be kept as a representative result.

Body composition: Lean mass and fat mass were measured by a bioimpedance analyzer Inbody520 (Biospace, Seoul, Korea). Specifically, for the area of abdominal adipose tissue, MRI (1.5 T, Siemens Avanto, Erlangen, Germany) were applied to conduct abdominal positioning scanning first, and then H-MRS detection. Sections will be acquired through the abdomen at the level of umbilicus to L4. Subcutaneous adipose tissue (SAT) and visceral adipose tissue (VAT) will be measured with NIH image software (ImageJ 1.41o; National Institutes of Health, Bethesda, MD, USA).

Blood samples in weeks 0 and week 12 were collected for metabolomics analysis. Feces samples in weeks 0 and week 12 were collected for detection of gut microbiome and gut microbiota-derived metabolites. Resting state cerebral functional magnetic resonance imaging was conducted before and after intervention to explore the effects of intervention on brain structure, network connectivity, and other parameters of brain functions.

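### No outcome reader or operator is masked in this open-label trial; fat-area, 1H-MRS and liver-stiffness measures are exposed, MRI-PDFF largely is not

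*Combined protocol and SAP*

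**What the plan says.** Section 3.1 sets the design: "This 12-week, open-label, randomized, controlled, parallel-group trial was conducted at Zhongshan Hospital Fudan University". The next section is headed "3.2 Randomization and masking". It covers a SAS-generated scheme, numbered envelopes and assignment in order of enrollment. Its only independence provision is that "randomization will be completed by staff unrelated to this trial", which protects allocation and not assessment. It ends with "The treatment will be carried out according to the arrangement of corresponding scheme" and names no masked party.

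Section 8 describes the measurements. For 1H-MRS, "A single 2×2×2 cm voxel was placed within the right lobe avoiding major vascular structures". For the abdominal fat areas, "Subcutaneous adipose tissue (SAT) and visceral adipose tissue (VAT) will be measured with NIH image software". Transient elastography uses a FibroScan M probe, with rules on the number and share of valid shots and on the interquartile range. MRI-PDFF liver and segment outlines come from a trained neural network.

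Section 6.1 gives the primary outcome as "Change in liver fat content from baseline to 12 months", without a measuring method. The aim in section 2 names MRI-PDFF. Visceral fat, subcutaneous fat and liver stiffness are listed in section 6.3.

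**The concern.** Nobody can conceal a 5:2 diet from the person eating it or from the nutritionist, so open-label delivery is not the criticism. Masked reading of outcomes was feasible, and the section whose heading promises it is silent. The protocol states a directional hypothesis in favour of intermittent restriction. Where a person places a voxel, draws a region or holds a probe, knowing the arm can push the result in the expected direction. Such a shift passes straight into the between-group difference. A larger sample does not remove it, and neither does the adjustment for age, sex and baseline in section 11.2.

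**Working it through.** The plan states no figure for assessor bias, so there is nothing to reproduce. The check has three parts.

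**1. Is anyone masked anywhere?** Sections 3.2, 8 (measurements), 9 (adverse events), 10 (data management), 11 (statistics) and 12 (quality control) contain no statement that an operator, reader or analyst is unaware of arm or visit.

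**2. Which measures leave room for human judgement?**

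| Measure | Place in section 6 | Human step in section 8 | Exposure |
|---|---|---|---|
| MRI-PDFF liver fat | Primary, if read with the aim | Outlines by neural network; manual correction is mentioned only for training data | Low |
| Glucose, HbA1c, enzymes, lipids, insulin | 6.2 and 6.3 | Laboratory assays and analysers | Low |
| Visceral and subcutaneous fat area | 6.3 | ImageJ; no automated procedure described, so operator-defined regions are inferred | Exposed |
| 1H-MRS liver fat | Not named; primary only if 6.1 is taken to include it | Voxel placement | Exposed |
| Liver stiffness | 6.3 | Probe acquisition, limited by validity and interquartile-range rules | Partly exposed |

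**3. When can the bias enter, and which comparison does it affect?** Section 7 and Table 2 put MRS, PDFF, elastography and body composition at V0 and week 12, with randomization at V1. Let Δ_I and Δ_C be the true mean changes in the intermittent and continuous arms. Let v be a week-12 shift from knowing the visit, common to both arms. Let b0 and b12 be the extra shifts in the intermittent arm, at baseline and week 12, from knowing the arm.

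- Between-group difference in change = (Δ_I + v + b12 − b0) − (Δ_C + v) = (Δ_I − Δ_C) + (b12 − b0). The visit shift v cancels.
- Paired before-after change in the continuous arm = Δ_C + v. Here v stays.
- At acquisition, b0 = 0 because V0 precedes randomization. The bias is then b12, and baseline adjustment leaves it in place. If V0 images are read off-line after randomization, b0 need not be 0.

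Masking to arm therefore protects the comparison of groups. Masking to visit mainly protects the paired tests of section 11.2.

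**What a shift would do if it existed (assumed values only).** Take the 8 in section 11.1 as the SD of liver fat change, with 30 per arm, or about 25 after the planned 15% dropout (30 × 0.85 = 25.5). For an unadjusted two-sample t test with no true difference, the noncentrality is b / (8 × √(2/n)). For b = 2 it is 2/2.263 = 0.884 at n = 25 and 2/2.066 = 0.968 at n = 30.

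| Assumed b (points) | Two-sided type I error, n = 25 to 30 per arm |
|---|---|
| 0 | 0.050 |
| 0.5 | 0.055 to 0.057 |
| 1 | 0.072 to 0.076 |
| 2 | 0.139 to 0.159 |
| 3 | 0.255 to 0.298 |

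The error grows with n. No entry is an estimate for this trial. On the liver fat scale the table matters only if MRS counts towards the primary outcome.

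**The case against.** The strongest reply is that the outcomes that matter most are hardly touched. The aim names MRI-PDFF, which a network segments; the blood measures in section 6.2 come from the laboratory; and the exposed listed outcomes sit in section 6.3. That stands, and it limits the point. The choice of PDFF sequence and summary statistic left open in section 8 is a matter of analysis flexibility, not masking. Waist circumference is taken by staff but is not a listed outcome. The FibroScan rules (at least 10 valid measurements, at least 60% valid, interquartile-range limits, median retained) restrict operator selection, although they do not mask the operator.

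A second reply is that silence about masking does not show that readers knew the arm. That also stands: a reader might infer that readers were in fact unmasked, but the documents only fail to say that they were masked.

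A third is that section 3.1 reports the trial as already conducted between July 2020 and July 2021, so acquisition can no longer be masked. This rules out part of any remedy, but not masked reading of stored images.

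**Conclusion.** The gap is real and narrow. Section 3.2 masks nobody and no other section fills the gap. The consequence is a possible arm-related bias in visceral and subcutaneous fat areas, 1H-MRS liver fat and, to a lesser extent, liver stiffness. It can arise only at week-12 acquisition and in off-line reading done after randomization.

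Two stronger readings are tempting. One is that the primary result is compromised. The documents do not support this while liver fat means MRI-PDFF; it becomes relevant only if section 6.1, which names no method, is taken to include MRS. The other is that the bias can be sized, for instance as a percentage of a fat area. The documents give no fat-area values, no SD for them and no reader error, so any such figure is assumption alone.

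The conclusion rests on one inference: that ImageJ areas involve operator-defined regions, since no automated procedure is described. This is a worthwhile low-cost improvement, not a threat to the main comparison.

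**What to change.** Add text of this kind to section 3.2 and repeat it in section 8:

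*Stored visceral and subcutaneous fat images and 1H-MRS spectra are exported under a study code without arm or date. The existing readers process them in random order, masked to arm and visit, before the allocation list is merged.*

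If reading is already done, re-read the stored files in this way and say so.

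Coded reading of spectra cannot undo a voxel placed with knowledge of arm, and it does not reach elastography. For these two, if week-12 acquisition is still to come, mask the operators to arm. If it is complete, state plainly that operators were not masked where that was so, and interpret MRS and stiffness differences accordingly. Masking text must not be added for something that did not happen.

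The cost is coding and random ordering of files, safe keeping of the code, and reading in batches instead of visit by visit. Re-reading, if needed, takes reader time. No extra reader or patient procedure is required.
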